Study treatment discontinuation	When the patient permanently stops taking any of the study drug(s) prior to the defined study treatment completion date (if any) for any reason; may or may not also be the point/time of study discontinuation.	
Treatment arm/group	A treatment arm/group defines the dose and regimen or the combination, and may consist of 1 or more cohorts.	
Variable (or endpoint)	The variable (or endpoint) to be obtained for each patient that is required to address the clinical question. The specification of the variable might include whether the patient experiences an intercurrent event.	
Withdrawal of consent	Withdrawal of consent from the study occurs when the participant explicitly requests to stop use of their data and/or biological samples AND no longer wishes to receive study treatment, AND does not agree to further protocol required assessments. This request should be in writing (depending on local regulations) and recorded in the source documentation.	
	This request should be distinguished from a request to discontinue the study. Other study participant's privacy rights are described in the corresponding informed consent form.	

Amendment 2 (Feb 2022)

Amendment rationale

Study was initiated in 19-Oct-2020. As of 31-Jan-2022, a total of 142 patients have been enrolled in the study. The slow enrollment of patients was impacted by the COVID-19 pandemic. This amendment is aimed to reduce the study sample size by modification of the statistical power of sample size calculation.

Changes in the protocol

Chapter	V01	V02	Reason
Protocol summary (Study design), Section 3, Section 5	275 HFrEF patients	219 HFrEF patients	Sample size is updated
Protocol summary – Exclusion criteria	2. Patients who received ARNI within 6 weeks prior to study	2. Patient received target dose (≥200 mg/d) of ARNI for 2 weeks continuously within the 6-week period prior to study enrollment.	Define 6-week period

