12.8 Sample size calculation

12.8.1 Primary endpoint

McNemar Test is used in the primary analysis to test for 2 correlated proportions. Approximate formula from Machin et al (1997) is used to calculate the minimum size required.

For the proportion of discordant pairs, the following approximate formula is used:

Proportion Discordant =
$$P_t(1 - P_s) + P_s(1 - P_t)$$

where P_t and P_s are proportion of patients experiencing the event of interest during ACEI/ARB and ARNI treatment period respectively. Over here, both proportions are assumed to be similar to de Diego et al (2018)'s study. According to de Diego et al (2018)'s study, SVT (one of the VA event) has the following incidence 8/120 and 1/120 during ACEI/ARB and ARNI treatment period respectively. Hence, by substitute both into the equation above, proportion discordant calculated is 0.0739 after rounding off.

For the difference, a parameter under effect size is approximated by the following formula:

Effect Size =
$$P_t(1 - P_s) - P_s(1 - P_t)$$

and after substituting P_t and P_s defined above, the effect size calculated is -0.0583.

Thus, by considering the parameters defined above, power of 0.8 and significance level of 0.05, the sample size required is 175. Further consider a dropout rate of 20%, the minimum sample size required is 219.

The above calculation is calculated using PASS 11 software's Test for Two Correlated Proportion (McNemar Test) [Differences] procedure.

For proportion of patients had ICD or CRT-D shocks occurrence over 6 months of ACEI/ARB and 6 months of ARNI treatment, the above sample size will provide 95% - 98% power to detect a proportion difference of 0.075 at two-sided significance level of 0.05. The proportion difference is derived from the published literature (de Diego et al 2018).

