12.8.2 Power for analysis of selected secondary variables

The following test of secondary variables are part of the global testing strategy.

Page 59 of 63 Protocol No. CLCZ696BCN04

For the paired differences of numbers of NSVT, SVT, ICD shocks and ATP over ACEI/ARB and ARNI treatment period, the above sample size will provide >95% power to detect mean of paired difference of at least -3 and standard deviation of at most 10. These are under the assumption of similar patient experiences as de Diego et al (2018)'s study.

For the change from date of treatment initiation after 6 months of treatment assessed by LVEF and NT-proBNP, the above sample size will provide 84% – 91% power to detect a treatment difference of 3 numeric values at the two-sided significance level of 0.05, assuming a standard deviation of 15.

13 Ethical considerations and administrative procedures

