3.2.2 Power for analysis of selected secondary variables

The following test of secondary variables are part of the global testing strategy.

For the paired differences of numbers of NSVT, SVT, ICD shocks and ATP over ACEI/ARB and ARNI treatment period, the above sample size will provide >95% power to detect mean of paired difference of at least -3 and standard deviation of at most 10. These are under the assumption of similar patient experiences as de Diego et al (2018)'s study.

For the change from date of treatment initiation after 6 months of treatment assessed by LVEF and NT-proBNP, the above sample size will provide 84% - 91% power to detect a treatment difference of 3 numeric values at the two-sided significance level of 0.05, assuming a standard deviation of 15.

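### The 84%–91% power stated for LVEF and NT-proBNP is not what 175–219 patients give (75%–84%); it matches 220–275 patients, the size of the design that Amendment 2 replaced

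*Protocol*

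**What the plan says.** Protocol section 12.8.1 sizes the trial on the McNemar test for SVT with power 0.8: "the sample size required is 175. Further consider a dropout rate of 20%, the minimum sample size required is 219". Section 12.8.2 then makes power claims for secondary variables at that same size. For LVEF and NT-proBNP it says "the above sample size will provide 84% – 91% power to detect a treatment difference of 3 numeric values". The inputs given with this claim are a two-sided 0.05 level and an SD of 15. SAP section 3.2.2, written for protocol Version 02, carries the same claim: "the above sample size will provide 84% - 91% power".

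Protocol section 12.5.2 and SAP section 7.4.2 plan a paired t-test for these changes, with the Wilcoxon signed-rank test if the data are not normal. The study has one arm, and each patient is compared with himself or herself across the two treatment periods.

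The rationale for Amendment 2 states: "This amendment is aimed to reduce the study sample size by modification of the statistical power of sample size calculation". Its change table shows planned enrolment falling from 275 to 219. It lists no revision of the power figures for LVEF and NT-proBNP.

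**The concern.** A power range tied to a stated sample size should reproduce from that sample size. This one has the look of a leftover: the trial became smaller by about a fifth, the primary calculation was redone, and the secondary power claim still reads as for a larger trial.

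The protocol describes these secondary tests as belonging to a global testing strategy, so the claim is not decorative. A non-significant LVEF or NT-proBNP result would be judged against a power the trial never had. Those who approved the reduction in size were also not shown what it did to these two endpoints.

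**Working it through.** **Inputs**

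- Difference 3, standard deviation 15, two-sided alpha 0.05: protocol 12.8.2, SAP 3.2.2.
- Evaluable n = 175, enrolled n = 219, dropout 20%: protocol 12.8.1, SAP 3.2.1.
- Superseded enrolment 275: Amendment 2 change table. The evaluable number for that design is not printed; 275 × 0.8 = 220.
- Test: paired t-test. The 15 is taken as the standard deviation of the within-patient difference, which the documents do not state explicitly.

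**Formula**

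Standardised effect = 3/15 = 0.2. Power = P(|T| > t(0.975, n−1)), where T is noncentral t with n−1 degrees of freedom and noncentrality 0.2·√n. The normal approximation is Φ(0.2·√n − 1.96).

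**Results**

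| n | 0.2·√n | Power, noncentral t | Normal approximation |
|---|---|---|---|
| 175 (current, evaluable) | 2.646 | 74.9% | 75.4% |
| 219 (current, enrolled) | 2.960 | 83.8% | 84.1% |
| 220 (superseded, evaluable, derived) | 2.966 | 84.0% | 84.3% |
| 275 (superseded, enrolled) | 3.317 | 91.1% | 91.3% |

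The plan's range reproduces at both ends for 220–275. For the current design it reproduces at neither end in its place: 84 − 74.9 = 9.1 points too high at 175, and 91 − 83.8 = 7.2 points too high at 219. The 84% given as the lower end is, to rounding, the power with full enrolment and no dropout. The type II error at 175 is 100 − 74.9 = 25.1%, against the 16% that 84% implies.

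**Does 220–275 fit the earlier primary calculation?**

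Exact McNemar power with the protocol's rounded inputs (discordant proportion 0.0739, difference 0.0583) is:

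- 80.2% at n = 175, and 175/0.8 = 218.75, rounded up to 219, the current design;
- 89.99% at n = 219 and 90.15% at n = 220, so 220 is the first size to reach 90%, and 220/0.8 = 275, the Version 01 enrolment.

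So 220 and 275 follow from the primary calculation at 90% power, independently of the LVEF claim.

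**Related figures**

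- Power of 80% for a difference of 3 needs 199 evaluable patients (198 gives just under 80%).
- With 175 patients, the difference detectable with 80% power is 3.19.
- The claim of more than 95% power for event counts (difference 3, standard deviation 10) still holds: 97.7% at 175.

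**The case against.** **Another reading of the inputs might rescue the range.** The sentence does not say whose standard deviation the 15 is. If it is the standard deviation within each period, and the within-patient correlation is 0.6, the standard deviation of the difference is 15·√(2 × 0.4) = 13.4, and power is 83.7% at 175 and 90.9% at 219, close to the printed range. But no correlation appears anywhere in the documents. Correlations of 0.3 to 0.7 would give 60% to 92% at 175 and 70% to 97% at 219. A one-sided 0.05 test gives 83.9% and 90.4%, but the text says two-sided. Either rescue needs an unstated parameter or contradicts the sentence. The ambiguity about the 15 stands and should be removed in the correction.

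**The link to the old design is inferred.** This stands. The Version 01 text of 12.8.2 is not available, and 220 is printed nowhere. The inference is strong, since both ends match and the primary calculation leads separately to 220 and 275. The numerical error does not depend on it.

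**It is only a supporting statement.** The sample size comes from the SVT calculation, and no test, estimate or analysis set uses the 84%–91%. The 0.8 target is set for the primary endpoint only; the plan names no minimum for secondary endpoints. This limits the consequences. It does not make the sentence correct.

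**A t-test figure may not apply.** If the Wilcoxon test is used, power under normality is slightly lower (72.9% and 82.1%, with relative efficiency 0.955). The difference of 3 and standard deviation of 15 are also given without units for both LVEF and NT-proBNP, although the NT-proBNP endpoint is a proportional change. Both are fair points, and both argue for rewriting the sentence.

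**Conclusion.** The stated power is wrong for the current design. With the inputs as printed, power for LVEF and NT-proBNP is 75%–84% across 175–219 patients, not 84%–91%. The overstatement is about 9 points at the evaluable number and 7 at the enrolled number. After the planned dropout, power is below the 0.8 used for the primary endpoint.

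This rests on a paired t-test, a two-sided 0.05 level, and 15 as the standard deviation of the within-patient difference. That the figures were carried over from the 275-patient design is a well-supported inference.

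The primary sample size and the power claim for event counts are not affected. The ICD-shock power range in 12.8.1 is not judged here, because the plan gives no discordant proportion for it.

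**What to change.** In protocol section 12.8.2 and SAP section 3.2.2, replace the 84%–91% range with 75%–84% and name the two sample sizes it refers to (175 and 219). Alternatively, state the difference detectable with 80% power at 175 patients: about 3.2 with standard deviation 15.

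In the same sentence, say that 15 is the standard deviation of the within-patient difference (or give the per-period value and the assumed correlation), name the test, and give the units separately for LVEF and for the proportional change in NT-proBNP. If the sponsor intended a different standard deviation or correlation, that assumption should be written down and the power recomputed from it.

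The cost is a reworded sentence in each document and a less favourable power statement. No patients, visits or analyses are added.

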13.1 Regulatory and ethical compliance

This clinical study was designed and shall be implemented, executed and reported in accordance with the ICH Harmonized Tripartite Guidelines for GCP, with applicable local regulations (including European Directive 2001/20/EC, US CFR 21), and with the ethical principles laid down in the Declaration of Helsinki.

13.2 Responsibilities of the investigator and IRB/IEC

Before initiating a trial, the investigator/institution must obtain approval/favorable opinion from the IRB/IEC for the trial protocol, written informed consent form, consent form updates, participant recruitment procedures (e.g., advertisements) and any other written information to be provided to patients. Prior to study start, the investigator is required to sign a protocol signature page confirming his/her agreement to conduct the study in accordance with these documents and all of the instructions and procedures found in this protocol and to give access to all relevant data and records to Novartis monitors, auditors, Novartis Quality Assurance representatives, designated agents of Novartis, IRBs/IECs, and regulatory authorities as required. If an inspection of the clinical site is requested by a regulatory authority, the investigator must inform Novartis immediately that this request has been made.

13.3 Publication of study protocol and results

The protocol will be registered in a publicly accessible database such as clinicaltrials.gov, In addition, after study completion (defined as last patient last visit) and finalization of the study report the results of this trial will be submitted for publication and posted in a publicly accessible database of clinical trial results.

For details on the Novartis publication policy including authorship criteria, please refer to the Novartis publication policy training materials that were provided to you at the trial investigator meetings.

13.4 Quality control and quality assurance

Novartis maintains a robust Quality Management System (QMS) that includes all activities involved in quality assurance and quality control, to ensure compliance with written Standard Operating Procedures (SOPs) as well as applicable global/local GCP regulations and ICH Guidelines

Audits of investigator sites, vendors, and Novartis systems are performed by auditors, independent from those involved in conducting, monitoring or performing quality control of the clinical trial. The clinical audit process uses a knowledge/risk based approach.

Audits are conducted to assess GCP compliance with global and local regulatory requirements, protocols and internal SOPs, and are performed according to written Novartis processes.

14 Protocol adherence

This protocol defines the study objectives, the study procedures and the data to be collected on study participants. Additional assessments required to ensure safety of patients should be administered as deemed necessary on a case by case basis. Under no circumstances including incidental collection is an investigator allowed to collect additional data or conduct any additional procedures for any purpose involving any investigational drugs under the protocol, other than the purpose of the study. If despite this interdiction prohibition, data, information, observation would be incidentally collected, the investigator shall immediately disclose it to Novartis and not use it for any purpose other than the study, except for the appropriate monitoring on study participants.

Investigators ascertain they will apply due diligence to avoid protocol deviations. If an investigator feels a protocol deviation would improve the conduct of the study this must be considered a protocol amendment, and unless such an amendment is agreed upon by Novartis and approved by the IRB/IEC and Health Authorities, where required, it cannot be implemented.

16.1 Appendix 1: Clinically notable laboratory values and vital signs

Clinically notable laboratory abnormalities for selected tests based on a percent change from baseline:

Hematology

Red blood cell (RBC) count, hemoglobin and hematocrit: >50% increase, >20% decrease

White blood cell (WBC) count: >50% increase, >50% decrease

Platelet: >75% increase, >50% decrease

Blood chemistry

Alanine Aminotransferase (ALT) and Aspartate Aminotransferase (AST): >150% increase

Blood Urea Nitrogen (BUN), creatinine and uric acid: >50% increase

Total bilirubin and alkaline phosphatase: >100% increase

Creatinine phosphokinase (CPK): >300% increase

Potassium: >20% increase, >20% decrease

Chloride and calcium: >10% increase, >10% decrease

7.5.1 Drug exposure	
7.5.1 Drug exposure7.5.2 Adverse events	
7.5.1 Drug exposure7.5.2 Adverse events7.5.3 Laboratory test results	
 7.5.1 Drug exposure 7.5.2 Adverse events 7.5.3 Laboratory test results 7.5.4 12-lead ECG 	
 7.5.1 Drug exposure 7.5.2 Adverse events 7.5.3 Laboratory test results 7.5.4 12-lead ECG 7.5.5 Holter 	
 7.5.1 Drug exposure 7.5.2 Adverse events 7.5.3 Laboratory test results 7.5.4 12-lead ECG 7.5.5 Holter 7.5.6 Echocardiogram 	
 7.5.1 Drug exposure 7.5.2 Adverse events 7.5.3 Laboratory test results 7.5.4 12-lead ECG 7.5.5 Holter 7.5.6 Echocardiogram 7.5.7 Vital signs 	
 7.5.1 Drug exposure 7.5.2 Adverse events 7.5.3 Laboratory test results 7.5.4 12-lead ECG 7.5.5 Holter 7.5.6 Echocardiogram 7.5.7 Vital signs 7.5.8 Physical examination 	

List of Abbreviations

Abbreviation	Explanation	
ACEI	Angiotensin-converting enzyme inhibitor	
AE	Adverse event	
ALT	Alanine aminotransferase	
ARB	Angiotensin receptor blockers	
ARNI	Angiotensin receptor neprilysin inhibitor	
AST	Aspartate aminotransferase	
ATC	Anatomical Therapeutic Chemical	
ATP	Anti-tachycardia pacing	
BID	Twice a day	
BMI	Body mass index	
BUN	Blood urea nitrogen	
СРК	Creatinine phosphokinase	
CRT-D	Cardiac resynchronization therapy-defibrillator	
DLT	Dose limiting toxicity	
DMP	Data management plan	
ECG	Electrocardiogram	
eGFR	Estimated glomerular filtration rate	
EOS	End of study	
GCP	Good Clinical Practice	
HF	Heart failure	
HFrEF	Heart failure with ejection fraction decreased	
ICD	Implantable cardioverter defibrillator	
ICF	Informed consent form	
LVEF	Left ventricular ejection fraction	
MedDRA	Medical Dictionary for Regulatory Activities	
mg	Milligram(s)	
mL	Milliliter(s)	
NSVT	Non-sustained ventricular tachycardia	
NT-proBNP	N-Terminal prohormone of Brain Natriuretic Peptide	
NYHA	New York Heart Association	
PVC	Premature ventricular contraction	
QD	Once a day	
QTcF	Fridericia QT correction formula	
RBC	Red blood cell(s)	
SAE	Serious adverse event	
SAF	Safety set	
SD	Standard deviation	
SVT	Sustained ventricular tachycardia	
TID	Three times a day	
ULN	Upper limit of normal	

VA	Ventricular arrhythmia	
VT/VF	Ventricular tachycardia/fibrillation	
WBC	White blood cell(s)	
WHO	World Health Organization	

1. Introduction

This Statistical Analysis Plan, prepared for "A multicenter, interventional, open-label and single-arm study to investigate the effect of ARNI on ventricular arrhythmia in HFrEF patients with ICD or CRT-D" (protocol number: CLCZ696BCN04) sponsored by Novartis, describes in detail the content and methods of statistical analysis.

This Statistical Analysis Plan is prepared based on the Study Protocol Version 02 dated March 15, 2022 and Case Report Form (CRF) Version 2.0 dated June 3, 2021.

2. Study Objectives

2.1 Primary Objective

The primary objective of this study is to assess the proportion of patients with VA events over 6 months of ACEI/ARB and 6 months of ARNI treatment.

2.2 Secondary Objectives

- To assess numbers of occurrences of VA events and ICD or CRT-D shocks over 6 months of ACEI/ARB and 6 months of ARNI treatment.
- To compare the changes in LVEF and NYHA level between ACEI/ARB and ARNI treatments
- To compare the changes in the NT-proBNP level between ACEI/ARB and ARNI treatments
- To compare the healthcare resource utilization of HF patients during ACEI/ARB and ARNI treatments

3. Study design

This will be a multicenter, interventional, open-label, and prospective single-arm study to evaluate the effect of ARNI on VAs in approximately 219 HFrEF patients receiving ICD or CRT-D in China.

After the informed consent process has been conducted and the patient has signed the informed consent form, baseline data will be collected. Implanted device data of patients will be collected for 12 months. ACEI/ARB therapy will be given to patients for 6 months. Dosage of ACEI/ARB will be based on investigator's discretion and up titrated after 2-4 weeks to the maximum dosage the patients can tolerate and according to product label.

[figure not shown]
After 6 months, patients using ACEI need to undergo a 36-hr washout period (36-hr washout period is not needed for patients using ARB at month 6). Patients will then receive ARNI (sponsored by Novartis only for this study) while the dosage of ARNI will be according to investigator's discretion and up titrated to the maximum dosage the patient can tolerate or 200

mg bid as per guideline. Table 3-2 lists the recommended starting dose of ARNI.

All patients will be followed up for 6 months for each treatment. After patients finalize the trial, the investigator will evaluate all patients and produce a report.

Study flow chart:

Figure 3-1 Study design

Abbreviations: ACEI = Angiotensin-converting enzyme inhibitor; ARB = Angiotensin receptor blockers; ARNI = Angiotensin receptor neprilysin inhibitor; EOS = End of Study Notes:

*Data collection at Baseline (0), Month 1, Month 3, Month 6, Month 7, Month 9, and Month 12 according to the evaluation schedule.

-Dosage and titration plan of ACEI/ARB and ARNI treatments will be according to investigator's discretion and product label (Please refer to Table 3-1 and Table 3-2).

-36-hr washout period is not needed for patients using ARB.

3.1 Patient numbering, treatment assignment, randomization

3.1.1 Patient numbering

Each patient is identified in the study by a Patient Number (Patient No. eight-digit code), that is assigned when the patient is first enrolled for screening and is retained as the primary identifier for the patient throughout his/her entire participation in the trial. The Patient No. consists of the Center Number (Center No. four-digit code) (as assigned by Novartis to the investigative site) with a sequential patient number suffixed to it, so that each patient is numbered uniquely across the entire database.

3.1.2 Treatment assignment, randomization

This is a single-arm study, no treatment assignment will be involved in this study. No randomization will be performed in this study.

3.1.3 Treatment blinding

Treatment will be open to patients, investigator staff, persons performing the assessments, and the clinical trial team (CTT).

3.2 Sample Size Calculation

3.2.1 Primary endpoint

McNemar Test is used in the primary analysis to test for 2 correlated proportions. Approximate formula from Machin et al (1997) is used to calculate the minimum size required.

For the proportion of discordant pairs, the following approximate formula is used:

Proportion Discordant = $P_t (1 - P_s) + P_s (1 - P_t)$

where P_t and P_s are proportion of patients experiencing the event of interest during ACEI/ARB and ARNI treatment period respectively. Over here, both proportions are assumed to be similar to de Diego et al (2018)'s study. According to de Diego et al (2018)'s study, SVT (one of the VA event) has the following incidence 8/120 and 1/120 during ACEI/ARB and ARNI treatment period respectively. Hence, by substitute both into the equation above, proportion discordant calculated is 0.0739 after rounding off.

For the difference, a parameter under effect size is approximated by the following formula:

Effect Size =
$$P_t (1 - P_s) + P_s (1 - P_t)$$

 P_t and P_s after substituting Pt and Ps defined above, the effect size calculated is 0.0583.

Thus, by considering the parameters defined above, power of 0.8 and significance level of 0.05, the sample size required is 175. Further consider a dropout rate of 20%, the minimum sample size required is 219.

The above calculation is calculated using PASS 11 software's Test for Two Correlated Proportion (McNemar Test) [Differences] procedure.

For proportion of patients had ICD or CRT-D shocks occurrence over 6 months of ACEI/ARB and 6 months of ARNI treatment, the above sample size will provide 95% - 98% power to detect a proportion difference of 0.075 at two-sided significance level of 0.05. The proportion difference is derived from the published literature (de Diego et al 2018).

